### **6.3 Safety Assessments**

Safety will be determined by an ongoing evaluation of the following:

- AEs
- Vital sign measurements
- ECGs
- Clinical laboratory tests
- Physical Examination
- COWS

#### **6.3.1 Medical History**

Medical histories will be obtained during screening (Part A and Part B) and will include demographic data (date of birth, sex, race, and ethnicity); histories of acute, chronic, and infectious disease; contraception use, surgical and oncologic histories; and any reported conditions affecting major body systems. All findings on medical history will be evaluated by the investigator for clinical significance.

The DSM-IV-TR modules will be used to screen for alcohol and substance dependence.

#### **6.3.2 Medication History and Recreational Drug and Alcohol Use**

All medications (prescription and non-prescription, herbal medications/natural health products, or investigational drugs) taken by the subjects during the 30 days prior to Screening (Part A and Part B) will be recorded in the source documentation as medication history.

A history of all drugs used for recreational/non-medicinal purposes (ie, psychoactive effects) and alcohol use will also be collected during the screening visit(s).

### 6.3.3 Physical Examination

A complete physical examination, assessing the subject's overall health and physical condition, will be performed at the Screening visit including height, weight, and BMI. Subsequent physical examinations will be performed per the Schedule of Events and may be performed by physicians or mid-level providers, such as advanced practice nurses and physician assistants, if they are appropriately licensed and credentialed to perform these examinations in accordance with local requirements and/or regulations.

Any clinically significant worsening after the start of study drug will be reported as an AE. Clinically significant findings observed prior to start of Study Drug treatment will be recorded as part of the medical history.

### 6.3.4 Electrocardiograms

12-Lead ECGs will be performed by the site and interpreted by the investigator or other appropriately credentialed designee. The ECGs will be performed with the electrodes positioned on the torso after the subject has been resting in a supine or semi-supine position for at least 3 minutes. The ECG will electronically measure and calculate ventricular heart rate and the PR, QRS, QT, QTcB, and QTcF intervals. The QTcF will be used for clinical evaluations.

### 6.3.5 Vital Signs

Vital signs will be measured after subjects have been at rest for approximately 3 minutes at the time points specified in the Schedule of Events. Vital signs will consist of systolic and diastolic blood pressure (mmHg), heart rate (bpm), and respiratory rate (breaths/min). Oral temperature (°C) will also be taken at some time points. In addition, pulse oximetry measurements will be taken with the vital signs monitoring system (eg, Dinamap) at designated time points and recorded after the continuous monitoring period (Section 6.3.6).

### 6.3.6 Continuous Pulse Oximetry

Continuous pulse oximetry will be performed by telemetry from pre-dose until at least 4 hours post-dose during the Qualification Phase in Part B and at least 6 hours post-dose during the Dose Selection Phase in Part A and the Treatment Phase in Part B, or longer, based on the discretion of the investigator or designee.

Continuous monitoring will include real-time measurements of SpO2. Oxygen saturation readings will be recorded at designated time points. After the continuous monitoring period, pulse oximetry measurements will be taken with the vital signs monitoring system (eg, Dinamap) at designated time points and recorded.

### 6.3.7 Columbia-Suicide Severity Rating Scale

The C-SSRS is a unique, simple, and short method of assessing both behavior and ideation that tracks all suicidal events, and provides a summary of suicidal ideation and behavior. It assesses the lethality of attempts and other features of ideation (frequency, duration, controllability, reasons for ideation, and deterrents), all of which are significantly predictive of completed suicide.

Two versions of the C-SSRS will be used in this study: the Baseline version assesses lifetime suicidal ideation and behavior, and the Since Last Visit version assesses suicidal thoughts or behaviors the subject may have had since the last time the C-SSRS was administered.

Occurrence of *suicidal ideation* after baseline is defined as having answered “yes” to at least 1 of the 5 suicidal ideation subcategories (ie, wish to be dead; non-specific active suicidal thoughts; active suicidal ideation with any methods [no plan] without intent to act; active suicidal ideation with some intent to act [without specific plan]; and active suicidal ideation with specific plan and intent) at any post-baseline evaluation. Occurrence of *suicidal behavior* after baseline is defined as having answered “yes” to at least 1 of the 4 suicidal behavior subcategories (ie, actual attempt, interrupted attempt, aborted attempt, and preparatory acts or behavior) at any post-baseline evaluation.

A trained rater will record the clinical observations on the scale, which will be used as the source document.

#### 6.3.8 Clinical Laboratory Assessments

Blood and urine samples will be collected, processed, and shipped according to the instructions provided in the laboratory manual. All laboratory safety data will be reviewed by the investigator or designee for clinical significance. See Section 9.4 for details regarding the anonymity of subject information.

Blood volumes required per laboratory test and study period/phase are provided in Appendix 11.1 (Part A) and in Appendix 11.2 (Part B).

**Clinical Chemistry:** Quantitative analysis will be performed for the following analytes: alkaline phosphatase, calcium, chloride, creatinine, random glucose, potassium, alanine aminotransferase, aspartate aminotransferase, gamma-glutamyl transpeptidase, sodium, total bilirubin, and urea.

**Hematology:** A peripheral blood smear will be performed to assess blood cell morphology. Quantitative analysis will be performed for at least the following analytes: hemoglobin, hematocrit, red blood cell (RBC) count, white blood cell (WBC) count, WBC differential (absolute counts), and numerical platelet count.

**Urinalysis:** Qualitative or quantitative analysis will be performed for the following analytes, as appropriate: specific gravity, pH, ketones, random glucose, nitrite, blood, leukocyte esterase, protein, urobilinogen, and bilirubin. If nitrite, blood, or protein tests are positive, a microscopic examination will be performed.

**Pregnancy:** Pregnancy tests for female subjects will test for the presence of  $\beta$ -Human Chorionic Gonadotropin (HCG) in blood serum or urine. Results of blood serum and urine pregnancy tests will be reported and determined to be negative prior to study continuation and/or dosing.

**FSH:** Post-menopausal status for female subjects, as applicable, will be confirmed by FSH testing at Screening.

**Viral Screen:** Serology will screen for hepatitis B, hepatitis C, and HIV. Only subjects with negative viral serology tests will be eligible for the study. Positive results will be managed according to local regulatory requirements.

**Breath Alcohol:** Breath alcohol testing will be performed. If there is any doubt or concern regarding alcohol use, research site staff may request a breath alcohol test at any time during the study.

**Drugs of Abuse Screen:** The urine drug screen will test for the following drugs of abuse: THC, oxycodone, other opiates (ie, the opiate panel will test for the presence of codeine, hydrocodone, hydromorphone, morphine, and oxymorphone), amphetamines (ie, amphetamine and methamphetamine), cocaine, and benzodiazepines. Refer to Section 4.8 for subject discontinuation rules in the event of a positive urine drug screen.

### 6.3.9 Clinical Opioid Withdrawal Scale

A sample form of the COWS is presented in Appendix 11.3.

#### 6.3.9.1 Treatment Phase Admission

At each admission to a Treatment period (Periods 1 through 7), subjects will undergo an assessment for signs or symptoms of withdrawal based on the COWS:

- Subjects with a COWS score  $< 5$  will be allowed to continue participating in the study period.
- Subjects with a COWS score  $\geq 5$  will be discontinued from the study and medically managed for at least 4 hours or longer until the investigator determines that the subject can be safely discharged from the CRU.

#### 6.3.9.2 Adhoc Assessments

The COWS may be administered adhoc during the Treatment Phase, at the investigator's discretion, based on any observed or reported AEs that may indicate signs or symptoms of withdrawal.

Subjects with an adhoc COWS score  $< 5$  will be allowed to continue participating in the study.

Subjects with an adhoc COWS score  $\geq 5$  will be discontinued from the study and medically managed for at least 4 hours or longer until the investigator determines that the subject can be safely discharged from the CRU.

### 6.3.10 Screening Assessments for Subjects who Participate in both Part A and Part B

Eligible subjects who participate in Part A may also participate in Part B (after informed consent to participate in Part B is obtained) and will only require re-screening (ie, completion of all screening assessments) if a duration of 60 days or greater has passed between the screening visit in Part A and the first visit (admission to the Qualification Phase) in Part B.

If a duration of at least 4 days but less than 60 days has passed from the screening visit in Part A and the first visit (admission to the Qualification Phase) in Part B, the following assessments will be performed for the subject:

- Blood samples will be collected for evaluation of hemoglobin, hematocrit, and liver enzymes (ie, ALT and AST) levels.
- Blood samples will be collected for HIV, hepatitis B and hepatitis C tests.
- Serum pregnancy test (females only).

#### 6.4 Appropriateness of Measures

The selected PD measures will assess positive and negative subjective drug effects associated with the abuse potential of a drug, as well as objective measures evaluating the cognitive and opiate effects. A number of concurrent measures will be used in this study to assess the abuse potential of nalbuphine relative to hydromorphone and placebo. These measures are grouped as follows:

- Measures of balance of effects (eg, rating of "at the moment" drug liking)
- Measures of global effects (eg, willingness to take the drug again)
- Measures of positive effects (eg, good effects, high)
- Measures of negative effects (eg, bad effects)
- Measures of stimulant and sedative effects (eg, drowsiness/alertness)
- Measures of perceptual disturbances (eg, hallucinations, Bowdle VAS)
- Measures of cognitive effects (eg, DAT, DSST, SSTM)
- Measure of opiate effect (eg, pupil size)

The selection of subjective abuse potential measures in this study, including the use of a bipolar Drug Liking VAS as the primary endpoint, is consistent with regulatory and literature guidelines. The assessment of drug liking has been chosen as the primary measure in the current study because the degree of subject liking is considered one of the most sensitive indices of abuse liability. The Drug Liking VAS and the Overall Drug Liking VAS assess slightly different aspects of drug liking. Drug Liking VAS assesses the subject's liking of the drug at the moment the question is asked, may be less subject to recall bias, and is useful for understanding the time-course of the effects. The Overall Drug Liking VAS is thought to assess 'global' drug effects (ie, subjective effects over the whole course of the experience including any carry-over effects), and has the additional advantage that the subject is generally sober by the time of the assessment (ie, end of day and/or next day). Other VAS items will measure positive, negative, and other subjective effects to assess the pharmacologic response to the study drugs. The Take Drug Again VAS will provide a global measure of drug effects and indicate the subject's willingness to take the drug again.

Pupillometry will be used as an objective physiological PD measure as it is a sensitive measure of central opioid action and appears to be resistant to tolerance development with repeated administration. Impairing effects will be evaluated on various measures of cognition evaluating divided attention, visual spatial processing speed, and short-term memory.

PK samples will be evaluated for plasma concentrations of nalbuphine. Standard safety assessments, such as AE reporting, vital signs (including oxygen saturation monitoring), physical examination, and ECGs will be included in this study.

## 7. ADVERSE EVENTS AND SERIOUS ADVERSE EVENTS

The investigator or designee and research site staff are responsible for the detection, documentation, classification, reporting, and follow-up of events meeting the definition of an AE or SAE.

Spontaneously reported or observed AEs will be recorded throughout the study, beginning at the time the subject gives informed consent. Subjects will be monitored throughout confinement for AEs and AEs may be elicited using a non-leading question at the discretion of the clinical staff. Regardless of seriousness, intensity, or presumed relationship to study drug, all AEs will be recorded in the source documentation from the time of first contact with the subject (eg, Screening) until the end of the Follow-up period of the study. AEs that occur after screening and prior to administration of the first dose of study drug will be recorded in the source documentation as baseline signs and symptoms. All measures required for management of AEs will be recorded in the source documentation.

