### **3.1.2 Dose Selection Study (Part A)**

Within 30 days of Screening, eligible subjects will enter the Dose Selection Phase that will include 1) a naloxone challenge to confirm that subjects are not opioid dependent, and 2) a dose escalation scheme to evaluate the safety and tolerability of single escalating oral doses of nalbuphine solution to non-dependent, recreational drug users.

During the naloxone challenge, subjects will receive 0.2 mg of naloxone via an intravenous (IV) bolus followed by 0.6 mg naloxone IV if no withdrawal signs are observed, as described in Section 4.4. The Clinical Opiate Withdrawal Scale (COWS) will be administered to confirm non-dependence. Subjects with a COWS score of <5 will be eligible to continue participation in the Dose Selection Phase.

At least 12 hours after completing the naloxone challenge, eligible subjects will receive a single oral dose of nalbuphine or placebo solution in a randomized, double-blind manner, after at least an 8-hour overnight fast, as described in Section 5.1.1. Each dosing cohort will comprise 8 unique subjects who will be randomized to nalbuphine or placebo in a ratio of 6:2 nalbuphine:placebo. All subjects within a cohort will receive the same dose of nalbuphine if randomized to active study drug.

At least 5 unique dosing cohorts are planned and the proposed single doses of nalbuphine solution will increase by at least 27 mg increments or will increase in an amount up to 50% of the dose administered in the previous cohort, as deemed appropriate by the safety and tolerability data: eg, 81 mg, 108 mg, 135 mg, 162 mg, and 243 mg (corresponding to 90 mg, 120 mg, 150 mg, 180 mg, and 270 mg of the HCl salt, respectively) or until an MSD is reached. Doses of nalbuphine solution are not to exceed 486 mg (ie, 3-fold the therapeutic dose). Dose reductions and intermediate doses may also be considered based on the results obtained in previous cohort(s). The rationale for the dosing cohorts planned is provided in Section 5.4, Selection of Doses.

Safety, PK, and PD (ie, pupillometry) assessments will be conducted for up to 24 hours after dosing or longer, at the discretion of the investigator or designee. Subjects will remain in the CRU until approximately 24 hours after administration of the study drug and after all final assessments are completed (or longer, at the discretion of the investigator or designee).

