Pharmacokinetics																	
Nalbuphine			Pre	0.25	0.5	1	1.5	2	2.5	3	4	5	6		8	10	12 24
Pharmacodynamics																	
Pupillometry			Pre	0.25	0.5	1	1.5	2	2.5	3	4	5	6		8	10	12 24
Study Administration																	
Naloxone Administration		X g															
Randomization			pre h														
Admission		X															
Study Drug Administration				0													
Discharge i																	X

AE=adverse event; BMI=body mass index; COWS=Clinical Opiate Withdrawal Scale; C-SSRS=Columbia-Suicide Severity Rating Scale; DSM-IV-TR=Diagnostic and Statistical Manual of Mental Disorders – Fourth Edition – Text Revision; ECG=electrocardiogram; FSH=follicle-stimulating hormone; HIV=human immunodeficiency virus; pre=pre-dose

e Oxygen saturation will be monitored continuously via telemetry for at least 6 hours post-dose or longer, if deemed necessary by the investigator or designee to ensure subject safety.

f Spontaneous AE reporting is continuous throughout the study; however, AE questioning may be performed using a non-leading question at discretion of the clinical staff.

g Naloxone challenge procedures are described in Section 4.4. For female subjects, the results of the urine pregnancy test are required prior to the naloxone challenge; results of the serum pregnancy test will not be required prior to the naloxone challenge.

h Day 1 only.

i Subjects will be discharged after assessments on Day 2 are complete and at the discretion of the investigator or designee to ensure subject safety.

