## 4.9 Dose Escalation Procedures and Stopping Criteria (Part A)

### 4.9.1 Data Review Committee

During the Dose Selection Phase in Part A, the safety data and, if available, PK data will be unblinded after completion of each dose cohort and reviewed by the DRC. The DRC will comprise, at a minimum, the sponsor representative, medical monitor (drug safety representative), and the investigator (or designee). Other representatives may be involved in data review and dose selection, as appropriate.

Dose escalation for the next cohort will proceed if the dose administered in the previous cohort was deemed to be safe and well tolerated by the DRC. The PK data will be unblinded and evaluated if available in a timely manner, but will not be required for dose escalation decisions. In addition, the results from the Dose Selection Phase will be reviewed and considered by the DRC for dose selection in the Treatment Phase in Part B.

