### 4.9.2 Dose Escalation and Stopping Rules

Dose escalation may proceed when the DRC have reviewed the available safety data for a cohort (and all preceding cohorts, as applicable) and agree that the safety profile supports proceeding with the evaluation of the next higher dose level. Escalation to the next dose level will continue until the MSD is identified (doses of nalbuphine solution will not exceed 486 mg, which corresponds to 3-fold the therapeutic dose) and only if it is supported by the safety data review by the DRC.

Dose escalation will be stopped if the following is observed in 3 or more subjects who received nalbuphine solution in a cohort experience the following AEs within 4 hours of dosing:

- Grade 3 or higher nausea or,
- Any episode of vomiting or,
- Grade 3 or higher somnolence

Furthermore, dose escalation will be stopped if any of the following is observed in at least 1 subject in a cohort who received nalbuphine solution:

- Sustained (~30 seconds) respiratory depression that results in SpO2 reduction below 92% that requires significant intervention (eg, naloxone administration).
- QTc prolongation (>500 ms or >60 ms above the baseline).
- Any Grade 3 or higher AE or an SAE that is considered by the investigator to be related to nalbuphine and clinically significant, or, any AE deemed by the investigator to be dose-limiting.

If the DRC observe a plateau in the incidence and severity of AEs, which do not meet the stopping criteria described above, then the PK data may be reviewed to determine if there is a plateau in the exposure of nalbuphine despite dose escalation. If a plateau is observed in the PK data, the MSD will be identified based on the available safety and PK exposure data.

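### Adverse-event questioning is optional and unscheduled, so low-grade AE counts may not be comparable across Part A cohorts of 6 or across Part B treatments

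*Protocol*

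**What the plan says.** Section 7 of the Protocol records AEs that are volunteered or observed, with subjects monitored during confinement, and adds that "AEs may be elicited using a non-leading question at the discretion of the clinical staff". Table 1 footnote f says the same for Part A: "AE questioning may be performed using a non-leading question at discretion of the clinical staff". Table 3 footnote i carries it into Part B, and SAP Table 2 footnote f copies it. Neither document sets questioning times, asks for the same approach in every cohort, or separates elicited from volunteered events. For concomitant medications, by contrast, Table 3 footnote h does fix specific questioning at admissions and follow-up.

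On Part A, Section 3.1.2 states: "Each dosing cohort will comprise 8 unique subjects who will be randomized to nalbuphine or placebo in a ratio of 6:2 nalbuphine:placebo". It also states: "All subjects within a cohort will receive the same dose of nalbuphine if randomized to active study drug". Planned doses are printed in Table 5.

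Section 4.9.2 has a plateau clause that begins "If the DRC observe a plateau in the incidence and severity of AEs, which do not meet the stopping criteria described above". In that case PK data may be reviewed, and if exposure has also levelled off, the MSD is set from safety and PK together. No numeric definition of a plateau is given. Sections 4.9.1 and 5.4.1 base the Part B solution doses on Part A results.

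**The concern.** Whether a mild symptom enters the database depends partly on whether someone asks about it. If asking is left to choice, it can vary by shift, by cohort or with what staff expect. A cohort asked less often looks better tolerated, and one asked more often looks worse.

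The events exposed to this are Grade 1 and 2 nausea, dizziness and somnolence. These are also the events from which a level dose-AE relation would be read. The rationale for Amendment 2 (Protocol Section 12.2) described the response up to 162 mg as flat, on mostly Grade 1 events in groups of 6, and used that to support larger dose steps. At stake is how far a flat low-grade profile can be trusted when the MSD and the Part B doses are chosen. In Part B the same discretion bears on AE incidence by treatment.

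**Working it through.** The documents give no figure for AE capture, and Part A cohort size rests on precedent alone (Protocol Section 8.2), so there is no stated number to reproduce. What follows is an illustration.

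**Inputs**
- Active subjects per cohort: n = 6 (Section 3.1.2).
- True share of subjects affected: 33% in one cohort and 50% in the next. These are assumptions.
- Relative capture d: the share of affected subjects recorded in the second cohort, relative to the first. Assumed range: two thirds to 1.

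**Formula**
X1 ~ Bin(6, 0.33) and X2 ~ Bin(6, 0.50 × d), independent. The chance of no apparent increase is P(X2 ≤ X1) = Σ P(X1 = a) × P(X2 ≤ a), for a = 0 to 6.

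**Equal capture (d = 1)**
The terms for a = 0 to 6 are 0.0014 + 0.0292 + 0.1132 + 0.1419 + 0.0711 + 0.0155 + 0.0013 = 0.374.

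**Unequal capture**

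| d | recorded rate, second cohort | P(no apparent increase) |
|---|---|---|
| 1 | 0.50 | 0.37 |
| 0.9 | 0.45 | 0.44 |
| 0.8 | 0.40 | 0.52 |
| 2/3 | 0.33 | 0.62 |

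The last row is a limiting case. Since 0.50 × 2/3 = 0.33, the assumed loss cancels the whole true rise, and 0.62 is what two cohorts with the same rate would give.

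**Other assumed rates**
- True rise from 30% to 45%: 0.40 with equal capture, 0.57 if capture falls from 100% to 75%, 0.74 if it falls to 50%, and 0.19 if it rises from 50% to 100%.
- True rise from 30% to 60%: 0.21, 0.40, 0.62 and 0.07 respectively.

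The distortion can thus hide a rise or exaggerate one.

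**Cohort size alone**
One subject is 1/6 = 17 percentage points of subject incidence. The exact 95% interval for 1 of 6 is 0.4% to 64%, and for 2 of 6 it is 4% to 78%. The 37% at equal capture is due entirely to n = 6. Unequal capture adds 7 points at d = 0.9 (44 − 37), 15 at d = 0.8 (52 − 37) and 25 at d = 2/3 (62 − 37).

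**The case against.** Four points stand against a stronger reading.

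1. AEs are also collected by observation. Subjects are confined, and dedicated nurses or paramedics monitor AEs around dosing (Section 4.7). Mild events were recorded under this method: 2 of 6 subjects had Grade 1 somnolence at 81 mg (Section 12.2). This stands. It reduces the likely loss, but does not make capture equal across cohorts.

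2. A reader might infer that the staff who question subjects know the cohort's dose. The inference is reasonable for the investigator: the DRC, on which the investigator or a designee sits, reviews unblinded data from earlier cohorts (Section 4.9.1), and Section 7 says "The investigator or designee and research site staff are responsible for the detection, documentation, classification, reporting, and follow-up". But no section says that bedside staff know the dose level, and active versus placebo stays masked until the cohort is complete (Section 5.5.1). The point does not need dose knowledge, since unscheduled questioning can vary without it.

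3. A reader might infer that AE counts decide the MSD. They do not decide it alone. The stopping criteria in Section 4.9.2 rest largely on vomiting, Grade 3 or higher events, SpO2 and QTc, which are unlikely to go unnoticed in monitored subjects. An apparent AE plateau only opens a PK review, and a PK plateau is needed before the MSD is set by that route. Low-grade events influence the DRC's judgement; they do not control it.

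4. A reader might infer that the cohorts are in fact not comparable. Nothing in the documents shows unequal capture. Discretion permits it, which is all that can be said.

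For Part B, questioning after every VAS battery would be a poor remedy: the scales repeat from 0.5 to 12 hours, so each question would precede the next Drug Liking rating, on which the primary endpoint rests.

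**Conclusion.** The concern holds in a limited form. AE questioning is left to choice in both documents, so low-grade AE counts may not be comparable across Part A cohorts of 6 or across Part B treatments. Those counts feed the plateau judgement, the MSD and the Part B doses as one input among several.

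Under the assumed 33% and 50% rates, a true rise goes unseen 37% of the time with equal capture and 44% to 62% of the time as relative capture falls from 90% to two thirds. The true rates and the capture values are assumptions. The 62% is the end of the range, not an expected value, and the fix does not touch the part due to n = 6.

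It is worth correcting because the change is small. SAP Sections 2.1 and 5 report that Part A is complete, that Part B had not begun, and that Part B will move to a new site, where different staff would exercise the same discretion.

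**What to change.** Amend Protocol Section 7 and the AE footnotes to Tables 1 and 3 so that every subject is asked the same open, non-leading question at fixed times, and flag each AE as spontaneous or elicited.

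- **Any dose-selection cohorts run as a new set:** ask at the scheduled vital-sign times. Part A has no subjective scales to prime.
- **Part B:** ask at admission, after the 12-hour VAS (the last on the dosing day), after the 24-hour VAS at discharge, and at follow-up. No question then falls within the 0.5 to 12 hour run of Drug Liking ratings. The 12-hour question does come before the 24-hour ratings, which include Overall Drug Liking and Take Drug Again; the amendment should acknowledge this.
- **Completed Part A:** collection cannot be changed. Report by cohort how AEs were elicited, if that was recorded, and qualify any plateau in low-grade AEs before relying on it for Part B.

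Cost: a protocol sentence, revised footnotes and one CRF field, with staff already present at these times. More mild AEs will be recorded, and Part B will rely partly on recall over the dosing day.
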